3.4.2 Safety Variables

Safety assessments will include monitoring and recording of solicited and unsolicited AEs, medically attended adverse events (MAAEs), AEs leading to discontinuation of the study vaccine/study withdrawal, SAEs, vital signs, and safety laboratory assessments.

3.4.2.1 Adverse Events

An AE is defined as any untoward medical occurrence associated with the use of a medicinal product in humans, whether or not considered related to the medicinal product. Adverse event collection will begin after the signing of informed consent and continue through study exit. Adverse events that occur prior to the administration of first dose of the study vaccine (i.e., non-study vaccine-emergent AEs) will be listed separately in the CSR.

An adverse event of special interest (AESI), including both serious and non-serious events, include myocarditis, pericarditis, and myopericarditis.

Adverse events will be collected on two distinct CRFs to capture solicited AEs and unsolicited AEs.

Solicited AEs refer to selected signs and symptoms occurring in the hours and days following a vaccination. These will be collected from participants on paper diary cards for seven consecutive days following each study vaccine administration. The following solicited AEs are included in the paper diary:

- Solicited local AEs: Injection site erythema, injection site pain, injection site induration/swelling, and injection site tenderness
- Solicited systemic AEs: Arthralgia, chills, diarrhea, dizziness, fatigue, fever (categorized by measured body temperature), headache, myalgia, and nausea/vomiting

The occurrence of each of these solicited AEs is regarded as vaccine-related AE. Solicited AEs are graded for severity according to the 5-point scales defined in the US FDA's Center for Biologics Evaluation and Research's Guidance: *Toxicity Grading Scale for Healthy Adult and Adolescent Volunteers Enrolled in Preventive Vaccine Clinical Trials* (2007).

Unsolicited AEs are defined as any spontaneously reported or discovered AE. Unsolicited AEs will be collected in all participants who receive at least one dose of the study vaccine and are classified according to the following:

- Mild, moderate, or severe;
- Whether or not the AE was categorized as an SAE, a MAAE, and/or an AE leading to discontinuation of the study vaccine/ study withdrawal; and
- Whether or not the AE was related to the study vaccine or the study procedure in the judgment of the Investigator.

3.4.2.2 Vital Signs and Pulse Oximetry

Vital sign parameters include heart rate (HR), blood pressure, respiratory rate, and body temperature. Vital signs will be collected as outlined in the clinical study protocol with participants in a semi-supine position after five minutes of rest. Results will be evaluated for clinical significance and any clinically significant change will be further evaluated for underlying cause and the associated AE will be reported if applicable. If no known cause is determined, the clinically significantly abnormal parameter may be reported as an AE.

Pulse oximetry will be collected as part of the solicitation of information relating to COVID-19 cases.

3.4.2.3 Laboratory Parameters

Clinical laboratory assessments will be collected as outlined in the clinical study protocol. The Investigator is responsible for reviewing and signing all laboratory reports. The signed clinical laboratory reports will serve as source documents and should include the Investigator's assessment of clinical significance of out of range/abnormal laboratory values.

3.4.2.4 Physical Examination

A complete physical examination will include, at a minimum, assessments of the general status of the participant, the skin of the intended study vaccine administration site, superficial lymph nodes, and cardiovascular, respiratory, gastrointestinal, and neurological systems.

A directed physical examination will include, at a minimum, assessments of the skin of the intended/actual study vaccine administration site and/or any organ systems relevant to symptoms or AEs reported by the participant.

3.4.2.5 Concomitant Procedures

A concomitant procedure is any therapeutic intervention (e.g., surgery/biopsy, physical therapy) or diagnostic assessment (e.g., blood gas measurement, bacterial cultures) performed between signing of the informed consent and the participant's last protocol-specified study visit.

All concomitant procedures must be recorded in the eCRF until 28 days after the last study vaccine. Thereafter, only concomitant procedures associated with an SAE, MAAE, AE leading to discontinuation of study vaccine/study withdrawal or treatment/evaluation of COVID-19 cases will be entered in the eCRF.

3.4.3 COVID-19 and SARS CoV-2 Infection Surveillance and Counseling

In concert with the collection of AEs, participants will be interviewed for potential symptoms of COVID-19 disease, recent diagnosis of SARS-CoV-2 infection, and for potential exposure to COVID-19. Potential symptoms of COVID-19 disease include, at a minimum, fever or chills, cough, shortness of breath or difficulty breathing, fatigue, muscle or body aches, headache, new loss of taste or smell, sore throat, congestion or

runny nose, nausea or vomiting, and diarrhea. Exposure to COVID-19 is defined as a participant who has had close contact (within 6 feet [2 meters] for a total of 15 minutes or more) to a person with laboratory-confirmed COVID-19 (or clinically compatible illness) or to a person who has tested positive for COVID-19 (laboratory confirmed) but has not had any symptoms.

Virologically confirmed COVID-19 cases occurring after study enrollment will be categorized by severity as defined by FDA criteria. Virologically confirmed cases are those cases with a positive laboratory test. The assessment of severity per FDA criteria is part of the Safety Review Committee (SRC) meetings, and will be performed for all cases where COVID-19 is confirmed. The assessment of severity per FDA criteria will be limited to confirmed COVID-19 cases, and will not be performed for suspected COVID-19 cases.

Compliance with counseling for long-term follow-up for SARS-CoV-2 infection will be provided for all participants who choose to terminate the study early. Participants will be told to inform the Investigator if they develop symptoms compatible with COVID-19 or a confirmed diagnosis of SARS-CoV-2 infection within 12 months after the last dose of the study vaccine.

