2.2 Exploratory Objectives and Endpoints

The exploratory objectives and endpoints are presented in [Table 3](#).

Table 3 Exploratory Objectives and Endpoints

Exploratory Objectives	Endpoint Description
1. To describe and to compare the cell-mediated immune response to different variants of SARS-CoV-2 viruses following vaccination with 3 investigational SARS-CoV-2 self-amplifying RNA vaccines	
Endpoint 1: CMI responses will be measured at designated time points using one or more of the following assays (Appendix 1 and Appendix 2):
 
a. ELISpot (Oxford Immunotec T-spot) assay.b. Intracellular Staining using Flow Cytometry (ICS, Oxford Immunotec)c. Fc effector function: Antibody-mediated cytotoxicity will be measured using surrogate assays measuring CD16 signaling at some or all time points designated in the Schedule of Assessments.d. Additional assays of CMI function may be performed and will be specified in the SAP prior to analysis.

Table 3 Exploratory Objectives and Endpoints

Exploratory Objectives	Endpoint Description
2. To summarize the incidence of COVID-19 cases in enrolled study participants	
Endpoint 2: Virologically confirmed COVID-19 cases occurring after study enrollment will be summarized according to the following:
 
a. Onset within the first 14 days after receipt of the first study vaccinationb. Onset at least 14 days after receipt of the first study vaccinationc. Severity (severe versus non-severe cases) as defined by FDA criteria
3. To provide sera for use for exploratory passive transfer studies in animals	
Endpoint 3: No formal analysis of endpoints will be performed in this study.

Abbreviations: CMI=cell-mediated immunity; COVID-19=Coronavirus disease 2019; ELISpot=enzyme-linked immune absorbent spot; FDA=Food and Drug Administration; RNA=ribonucleic acid; SAP=statistical analysis plan; SARS-CoV-2=severe acute respiratory syndrome coronavirus 2.

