6.7 Surveillance for SARS-CoV-2 Infection

In concert with the collection of AEs, participants will be interviewed for potential symptoms of COVID-19 disease, recent diagnosis of SARS-CoV-2 infection, and for potential exposure to COVID-19. The assessment of causality and severity for COVID-19 events will be evaluated in accordance with practices for other unsolicited adverse events.

Potential symptoms of COVID-19 disease include, at a minimum, fever or chills, cough, shortness of breath or difficulty breathing, fatigue, muscle or body aches, headache, new loss of taste or smell, sore throat, congestion or runny nose, nausea or vomiting, and diarrhea.

Exposure to COVID-19 is defined as a participant who has had close contact (within 6 feet [2 meters] for a total of 15 minutes or more) to a person with laboratory-confirmed COVID-19 (or clinically compatible illness) or to a person who has tested positive for COVID-19 (laboratory confirmed) but has not had any symptoms.

This is irrespective of whether the person with COVID-19 or the contact was wearing a mask or whether the contact was wearing respiratory personal protective equipment (PPE).

Participants should be reminded to contact the site within 24 hours if experiencing COVID-19-like symptoms or if exposed to a confirmed COVID-19 case.

Evaluation of participants with suspected COVID-19:

6. If a participant reports symptoms of potential COVID-19, an unscheduled clinic visit should occur within 48 hours
 - a. Reported symptoms include at a minimum: fever, chills, cough, shortness of breath or difficulty breathing, fatigue, muscle or body aches, headache, new loss of taste or smell, sore throat, congestion or runny nose, nausea or vomiting, and/or diarrhea.
 - b. An exception to this is if the potential symptoms of COVID-19 are observed within 7 days following study vaccination AND the Investigator determines that these symptoms are more consistent with vaccine adverse reactions and not COVID-19 symptoms.
 - c. If local policy does not allow an unscheduled in-person clinic visit, a RT-PCR or rapid antigen test may be performed and a telemedicine visit will be conducted. Alternatively the site can bring the test kit to point of care for sample collection and perform a telemedicine visit.
7. If a participant reports a potential exposure to COVID-19, an unscheduled clinic visit should be performed within 48 hours

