APPENDIX 7 CASE DEFINITIONS FOR COVID-19

Primary Case Definition (Based on FDA recommendation [DHHS 2020])

Case Definition	Laboratory Finding*	Clinical Status	
		Symptoms	Other Clinical Parameters
Uninfected	No positive SARS-CoV-2 test	None	None relevant
Asymptomatic SARS-CoV-2 Infection	Positive SARS-CoV-2 test	None	None relevant
Protocol-defined COVID-19	Positive SARS-CoV-2 test	At least one of the following that is a NEW or WORSENING finding: Fever or chills Cough Shortness of breath or difficulty breathing Fatigue Muscle or body aches Headache New loss of taste or smell Sore throat Congestion or runny nose Nausea or vomiting Diarrhea	None relevant
Atypical COVID-19	Positive SARS-CoV-2 test	Clinical findings suggestive of COVID-19 but not included in the row above	None relevant
Severe COVID-19	Positive SARS-CoV-2 test	As above for protocol-defined COVID-19	Any of the following: 
• Clinical signs at rest indicative of severe systemic illness:
- Respiratory rate ≥ 30 per minute,- Heart rate ≥ 125 per minute,- $\text{SpO}_2 \leq 93\%$ on room air at sea level or $\text{PO}_2/\text{FiO}_2 < 300$ mm Hg

Case Definition	Laboratory Finding*	Clinical Status	
		Symptoms	Other Clinical Parameters
			
 • Respiratory failure (defined as needing high flow oxygen, noninvasive ventilation, mechanical ventilation or ECMO) • Evidence of shock: 
 - SBP <90 mm Hg, or - DBP <60 mm Hg, - or requiring vasopressors • Significant acute renal, hepatic, or neurologic dysfunction • Admission to an ICU • Death

Abbreviations: COVID-19=coronavirus disease 2019; DBP=diastolic blood pressure; ECMO=extracorporeal membrane oxygenation; FiO₂=fraction of inspired oxygen; ICU=intensive care unit; pO₂=partial pressure of oxygen; SARS-CoV-2=severe acute respiratory syndrome-coronavirus-2; SBP=systolic blood pressure; SpO₂=oxygen saturation.

Alternate Case Definition for Grading of Severity of SARS-CoV-2 Infection/COVID-19 (Based on World Health Organization recommendation [WHO 2020c])

Case Definition	Lab Finding*	Clinical Status	Other Clinical Parameters	Score
Uninfected	No positive SARS-CoV-2 test	N/A	N/A	0
Mild Disease	Positive SARS-CoV-2 test	Ambulatory	Asymptomatic	1
			Symptomatic; independent	2
			Symptomatic; assistance needed	3

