4.7 COVID-19 and SARS-COV-2 Infection Surveillance and Counseling

The incidence rate of virologically confirmed COVID-19 cases occurring after study enrollment will be summarized for each cohort by study vaccine group and severity (severe vs. non-severe) as defined by FDA criteria for the mITT. The incidence rate will be calculated in person-days, where incidence rate is calculated as shown below:

Incidence rate = (COVID-19 cases) / (Number of Participants \times Timeframe).

The timeframes that will be considered are onset within first 14 days after receipt of the first study vaccination and onset 14 days after receipt of first study vaccine. Surveillance time will be censored at the time of first event or at the time of receipt of off-study COVID-19 vaccine (per mITT definition).

A sensitivity analysis will be repeated to include both suspected and confirmed cases of COVID-19 for each Cohort or Sub-cohort by study vaccine group.

Data collected in response to COVID-19 and SARS-CoV-2 infection surveillance questionnaires and counseling will be presented in participant data listings.

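### The SAP identifies a confirmed COVID-19 case by a positive test without carrying over the symptom requirement of protocol Appendix 7, so asymptomatic infections can be counted as non-severe COVID-19

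*SAP*

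**What the plan says.** Exploratory objective 2 (protocol 2.2) concerns the incidence of COVID-19. The endpoint reads "Virologically confirmed COVID-19 cases occurring after study enrollment will be summarized according to the following", followed by two onset windows around Day 14 and severity by FDA criteria. Section 2.2 does not itself define a COVID-19 case.

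The protocol defines it in Appendix 7. The primary, FDA-based table has a row headed "Asymptomatic SARS-CoV-2 Infection", with a positive test and no symptoms. Protocol-defined COVID-19 is a different row, which needs a positive test and "At least one of the following that is a NEW or WORSENING finding". Atypical COVID-19 needs a positive test and other suggestive clinical findings. Severe COVID-19 needs the symptoms of the protocol-defined row plus a severity criterion.

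SAP 3.4.3 says "Virologically confirmed cases are those cases with a positive laboratory test". It then uses the FDA criteria for severity only: "The assessment of severity per FDA criteria will be limited to confirmed COVID-19 cases, and will not be performed for suspected COVID-19 cases". SAP 4.7 states that the incidence rate "will be summarized for each cohort by study vaccine group and severity (severe vs. non-severe) as defined by FDA criteria for the mITT". Surveillance time stops at the first event or at receipt of an off-study COVID-19 vaccine. The sensitivity analysis adds suspected cases to confirmed ones.

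On detection, protocol 6.7 says "If a participant reports a potential exposure to COVID-19, an unscheduled clinic visit should be performed within 48 hours". The same section ends the follow-up calls of an asymptomatic exposed participant at a negative RT-PCR or rapid antigen result, so such participants are tested. SAP 3.1 also says that exposed participants are tested.

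**The concern.** The endpoint is meant to describe disease, but the SAP's only stated criterion describes infection. A programmer who applies SAP 3.4.3 as written has no instruction to look at symptoms, and SAP 4.7 provides no category for a positive test without them. The reported rate could then mix disease with infections found through exposure testing. It would depend partly on how often participants report exposures.

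The event definition also drives the denominator. If an asymptomatic positive is the first event, it ends that participant's surveillance time, and a later symptomatic episode in the same person drops out of the rate.

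**Working it through.** The documents give no figure to reproduce here: no expected case count, no asymptomatic share and no sample-size calculation. The check is mainly a comparison of texts.

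**Step 1: follow one asymptomatic positive through each document.**

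| Question | Protocol Appendix 7, primary table | SAP 3.4.3 and 4.7, read literally |
|---|---|---|
| Is it a COVID-19 case? | No; it has its own infection row | Yes; the test is positive |
| Severity class | Not applicable; the severe row requires symptoms | Non-severe, the only class left |
| Does it end surveillance time? | Not addressed in Appendix 7 | Yes, as the first event |
| Is it shown separately? | Yes, as a separate category | No planned summary row; listings only |

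**Step 2: can such positives arise?** Yes. Protocol 6.7 and SAP 3.1 both provide for testing after exposure without symptoms. The documents do not say how many to expect.

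**Step 3: does any other planned analysis correct for it?** No. The sensitivity analysis in SAP 4.7 widens the definition by adding suspected cases; nothing narrows it to the Appendix 7 definition. The windows in SAP 4.7 are set by onset, and the SAP does not say what date serves as onset when there are no symptoms.

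**Step 4: size of the effect on the count.** Let N be the number of participants with a positive test and s the share who are asymptomatic. The literal rule counts N and Appendix 7 counts N(1-s), so the inflation is N / [N(1-s)] = 1/(1-s).

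| Assumed s | 1/(1-s) |
|---|---|
| 10% | 1.11 |
| 20% | 1.25 |
| 30% | 1.43 |
| 40% | 1.67 |
| 50% | 2.00 |

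Every value of s is an assumption. The formula treats each participant as having one episode. A participant who is positive without symptoms and later falls ill is one case under either rule, but the literal rule dates the case to the earlier event.

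**Step 5: what one such participant does in a small group.** Cohort B has 36/3 = 12 planned per vaccine and Sub-cohort A1 has 12/3 = 4. Using the SAP 4.7 formula over the first 14 days, before any censoring, one asymptomatic positive changes the rate from 0 to 1/(12 × 14) = 1/168 = 0.0060 per person-day in a Cohort B group. In an A1 group it changes from 0 to 1/(4 × 14) = 1/56 = 0.018.

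**Step 6: which test confirms a case?** Appendix 7 describes laboratory confirmation by RT-PCR or an equivalent nucleic acid test. Protocol 6.7 also accepts rapid antigen tests. SAP 3.4.3 asks for a positive laboratory test without naming the type. The three passages do not settle whether an antigen-only positive is a confirmed case.

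**The case against.** The best defence is that SAP 3.4.3 explains only the words virologically confirmed. The sentence before it already speaks of COVID-19 cases, and the paragraph goes on to contrast confirmed with suspected cases. On that reading the protocol still supplies the meaning of COVID-19. SAP 4.10 supports this by declaring no change from the protocol's planned analyses, and the FDA criteria that the SAP names appear in Appendix 7 as the table that separates asymptomatic infection. This reading is possible, so it would go too far to say that the SAP orders asymptomatic positives to be counted. It does not remove the problem: the sentence is the SAP's only case criterion, it cites nothing, and two programmers could reach different counts.

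A second objection is that Appendix 7 also contains an "Alternate Case Definition for Grading of Severity of SARS-CoV-2 Infection/COVID-19", WHO-based, which scores an asymptomatic positive as mild disease. That is correct, so the symptom requirement belongs to the primary table and not to all of Appendix 7. However, the endpoint and the SAP both name FDA criteria, and the SAP does not use the WHO scale.

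A third is that the consequence is small. The endpoint is exploratory, about 72 participants are planned, no formal group comparison is made, and surveillance data are listed by participant, so a reader of the listings could separate the infections. All of this stands and limits the severity.

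A reader might also infer from the wording of SAP 4.7, which refers to each cohort for the main rate and mentions sub-cohorts only for the sensitivity analysis, that A1 and A2 are to be pooled. The documents do not support that. SAP 4.1.1 requires Cohort A tables and figures by sub-cohort and vaccine group, and summarizing by cohort is the SAP's routine shorthand in 4.5.2, 4.6.1, 4.6.2, 4.6.4 and 4.6.5.

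**Conclusion.** The point holds as a gap in the SAP's case definition. The stated criterion omits the symptom requirement of Appendix 7's primary table. With exposure testing and a two-way severity split, asymptomatic infections, if detected, can be reported as non-severe COVID-19 and can end surveillance time.

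The size cannot be determined from the documents. The factor 1/(1-s) gives the form of the effect, but s is assumed. A reader might infer that asymptomatic positives are bound to occur; the documents show only that the testing plan can find them. No primary objective is affected, and the change is worth making mainly because it is cheap and prevents a count that conflicts with the protocol.

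**What to change.** In SAP 3.4.3, replace the criterion with a definition along these lines: *a virologically confirmed COVID-19 case is a participant who meets the protocol-defined, atypical or severe category of the primary table in protocol Appendix 7, that is, a positive SARS-CoV-2 test together with the clinical findings of that category.*

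In SAP 4.7:

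- use this definition for the rate and for the event that ends surveillance time;
- report asymptomatic SARS-CoV-2 infection as its own row;
- state how a participant who tests positive without symptoms and later develops them is classified and dated.

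Reconcile Appendix 7, protocol 6.7 and SAP 3.4.3 on whether a rapid antigen result confirms a case.

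Leave the rule in SAP 4.5.1 unchanged. It censors immunogenicity data at confirmed infection, and the narrower disease definition should not be carried into it, because an infection without symptoms can also alter antibody levels.

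The cost is SAP wording and one extra table row. Protocol 6.3.1.2.15 already sends symptom and exposure reports to a dedicated eCRF, so new data collection appears unnecessary. The downside is a COVID-19 count that is smaller, or at most equal, on an exploratory, descriptive endpoint that will already have few events.

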3.5 Data Quality Assurance

Report summaries will be generated using validated Base SAS® software, version 9.4 or higher, on a PC or server-based platform. Additional validated software may be used to generate analyses, as needed.

All SAS programs that create outputs or supporting analysis datasets will be validated by a second statistical programmer or biostatistician. At a minimum, validation of programs will consist of a review of the program log, review of output or dataset format and structure, and independent confirmatory programming to verify output results or dataset content. Additionally, all outputs will undergo a review by a senior level team member before finalization.

The content of the source data will be reviewed on an ongoing basis by project statistical programmers and statisticians. Data will be checked for missing values, invalid records, and extreme outliers through defensive programming applications, analysis-based edit checks, and other programmatic testing procedures. All findings will be forwarded to the project data manager for appropriate action and resolution.

